5.2.3 Pregnancies

To ensure patient safety, each pregnancy in a patient on study treatment must be reported to the Sponsor within 24 hours of learning of its occurrence. The pregnancy must be followed up to determine outcome, including spontaneous or voluntary termination, details of the birth, and the presence or absence of any birth defects, congenital abnormalities, or maternal and/or newborn complications. Pregnancy should be recorded on a Clinical Study Pregnancy Form and reported by the investigator to the Sponsor. Pregnancy follow-up should be recorded on the same form and must include an assessment of the possible relationship to the study treatment of any pregnancy outcome. Any SAE experienced during pregnancy must be reported on the SAE Report Form. Pregnancy outcomes must be collected for the female partners of any males who took study treatment in this study. Consent to report information regarding these pregnancy outcomes should be obtained from the mother.

5.2.4 Recording of Adverse Events

At each contact with the subject during the adverse event recording period (defined in [Section 5.2.1](#)), the investigator must seek information on adverse events by specific questioning and, as appropriate, by examination. Information on all adverse events should be recorded immediately in the source document, and in the appropriate adverse event module of the case report form (CRF). All clearly related signs, symptoms, and abnormal diagnostic procedures results should be recorded in the source document, though should be grouped under one diagnosis. To the extent possible, adverse events should be recorded as a diagnosis and symptoms used to make the diagnosis recorded within the diagnosis event. Do not list symptoms if a diagnosis can be assigned.

Conditions that were already present at the time of informed consent should be recorded in the Medical History CRF. Any condition listed in a subject's medical history for which the severity increases at the time of, or post-Descartes-11 infusion, should be captured as an adverse event.

Adverse events (including lab abnormalities that constitute AEs) should be described using a diagnosis whenever possible, rather than individual underlying signs and symptoms. When a clear diagnosis cannot be identified, each sign or symptom should be reported as a separate Adverse Event. The clinical course of each event should be followed until resolution, stabilization, or until

it has been determined that the study treatment or participation is not the cause. As detailed as possible, each adverse event should be evaluated to determine:

- The severity grade (CTCAE Version 5.0 Grade 1-5)
- Its duration (start and end dates)
- Its relationship to the study treatment: Is there a reasonable possibility that the AE is related to Descartes-11- No (unrelated) or Yes. If yes- is the event definitely, probably, possibly or unlikely related to the investigational treatment (Descartes-11).
- Action taken with respect to study or investigational treatment (none, dose adjusted, temporarily interrupted, permanently discontinued, unknown, not applicable)
- Whether medication or therapy taken (i.e., no concomitant medication/non-drug therapy, concomitant medication/non-drug therapy)
- Whether it is serious, as defined in [Section 5.1](#).

All adverse events should be treated appropriately. If a concomitant medication or non-drug therapy is given, this action should be recorded on the Adverse Event CRF. Adverse events should be entered into the eCRF system within 10 working days from the knowledge of the event took place. Once an adverse event is detected, it should be followed until its resolution or until it is judged to be permanent, and assessment should be made at each visit (or more frequently, if necessary) of any changes in severity, the suspected relationship to the study treatment, the interventions required to treat it, and the outcome.

Progression of malignancy (including fatal outcomes), documented appropriately in the medical records, should not be reported as a serious adverse event. Adverse events that occur concurrently with the progression of malignancy but that are not related to disease progression (i.e., deep vein thrombosis) will be reported as an adverse event as described above.

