4.5 Criteria for Removal from Protocol Therapy and Off-Study Criteria

4.5.1 Criteria for Removal from Descartes-11 Therapy

Off-treatment criteria mainly apply to eligibility for potential repeat Descartes-11 treatments. Completion of each cycle includes a response assessment visit. Patients will be taken off treatment for the following:

- General or specific changes in the patient's condition render the patient unacceptable for further treatment on this study in the judgment of the investigator.
- Any Descartes-11-related Grade 3 to 5 toxicity occurring within the 14 days immediately after infusion of the drug product, with the following exceptions:
 - \leq Grade 3 to 4 Tumor Lysis Syndrome (TLS) lasting <7 days
 - Grade 2 CRS associated with fever, hypotension or hypoxia lasting less than 72 hours (i.e., improves to \leq Grade 1 CRS in less than 72 hours)
 - Non-hematologic toxicities:
 - Fever of any grade, including febrile neutropenia
 - \leq Grade 3 diarrhea lasting <72 hours
 - \leq Grade 3 nausea and/or vomiting lasting <72 hours
 - \leq Grade 3 fatigue lasting <7 days
 - \leq Grade 4 transaminase, bilirubin, blood urea nitrogen (BUN), or creatinine elevation lasting <7 days
 - Hematologic toxicities:
 - \leq Grade 3 neutropenia of any duration or Grade 4 neutropenia lasting <28 days
 - \leq Grade 3 anemia of any duration or Grade 4 anemia lasting <28 days
 - \leq Grade 3 thrombocytopenia of any duration or Grade 4 thrombocytopenia lasting <28 days
 - All cytopenias except neutropenia, anemia, and thrombocytopenia as described above

The National Cancer Institute Common Terminology Criteria for Adverse Events (NCI CTCAE) Version 5 will be used to grade toxicities during the trial unless specified above.

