5.1.2 Suspected Adverse Reaction

Suspected adverse reaction means any adverse event for which there is a reasonable possibility that the test article caused the adverse event. For the purposes of IND safety reporting, "reasonable possibility" means there is evidence to suggest a causal relationship between the test article and the adverse event. A suspected adverse reaction implies less certainty about causality than adverse reaction, which means any adverse event caused by a test article.

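### The causality item files 'unlikely related' under Yes to a reasonable possibility, against the protocol's own definition, and section 4.5.1 does not say which causality grades count as related

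*Combined protocol and SAP*

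**What the plan says.** Section 5.2.4 sets a two-step causality item. The first step is "Is there a reasonable possibility that the AE is related to Descartes-11- No (unrelated) or Yes". The second step, reached only after Yes, grades the event as "definitely, probably, possibly or unlikely related to the investigational treatment". Only the No answer carries the label unrelated.

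Section 5.1.2 defines a suspected adverse reaction by the same phrase. For IND safety reporting, it says that a reasonable possibility "means there is evidence to suggest a causal relationship between the test article and the adverse event".

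Other places where relatedness matters, or might be expected to:

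- Section 5.2.5.3 bases the sponsor's 7-day and 15-day reports to the FDA on suspected adverse reactions that are unexpected and serious.
- Section 4.5.1 lists, among the reasons for removal from therapy, "Any Descartes-11-related Grade 3 to 5 toxicity occurring within the 14 days immediately after infusion of the drug product", followed by a list of exceptions. It names no causality grade and does not refer to section 5.2.4.
- Section 5.5 pauses the study after Grade 4 vital-organ events in two subjects, and counts only events assessed as probably or definitely related.
- Section 5.2.5 sends every serious event to the sponsor whatever its suspected cause.
- Appendix B, section 4.2.4, repeats the two-step item for the leukapheresis procedure, again with unlikely under Yes.

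**The concern.** The two steps can give contradictory answers. To reach the grade *unlikely*, the investigator must first say that a reasonable possibility exists, which section 5.1.2 equates with evidence pointing to causation. An investigator who thinks a link improbable must choose between Yes/unlikely and No/unrelated, and the protocol gives no rule for choosing. Two sites with the same clinical opinion can record opposite answers to the first question.

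At stake is the meaning of the word related. The Yes/No answer is the natural split for a table of related adverse events, and it matches the phrase that defines a suspected adverse reaction. In an open-label study with a single treatment regimen, no comparison group is available against which a difference in coding habits would show up. Removal from therapy also turns on relatedness, and section 4.5.1 leaves the threshold open.

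**Working it through.** No arithmetic applies. The check follows one event, graded *unlikely*, through each rule that might depend on causality.

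1. **Causality item (5.2.4).** The grade can be reached only through Yes. The event is therefore on the related side of the first question and does not carry the label unrelated.
2. **Definition (5.1.2).** Yes means that there is evidence to suggest causation; *unlikely* says that the investigator does not think the link probable. The two statements fit together poorly, and the protocol does not explain how both can hold.
3. **Expedited reporting (5.1.2 with 5.2.5.3).** Because the first answer is Yes, the event literally meets the suspected-adverse-reaction wording. It would become an expedited report only if it were also serious and unexpected.
4. **Removal from therapy (4.5.1).** The trigger is "Any Descartes-11-related Grade 3 to 5 toxicity" within 14 days after infusion, outside the listed exceptions. If related means any Yes, the event counts; if a higher grade is meant, it does not. The text does not decide. Infusions are planned for Days 1, 4, 8, 11, 15 and 18 (section 3.2.1), and 1 + 14 = 15, so the 14-day window after the first infusion reaches later planned infusions.
5. **Grade 4 pause rule (5.5).** The event does not count, because the rule names its own grades: probably or definitely.
6. **Reporting of serious events to the sponsor (5.2.5).** No effect, because causality plays no part.
7. **Cell collection (Appendix B, 4.2.4).** The same nesting appears, and Appendix B, section 4.1.2, repeats the definition in 5.1.2. The structure therefore occurs twice and is not an isolated slip.

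Steps 1 to 3 follow from the text. Step 4 depends on a reading that the text leaves open. Steps 5 and 6 show no effect.

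**The case against.** The strongest reply is that the flaw may do little harm.

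- An investigator who follows section 5.1.2 and sees no evidence of causation will answer No and never reach the second step, so few events may be coded Yes/unlikely. This is fair, and the documents give no count. But it also confirms that the grade has no proper place under Yes.
- Section 5.1.2 says that a suspected reaction implies less certainty than an adverse reaction, and its definition is expressly for IND reporting. Both are true. The bar is low, but it still asks for evidence, and section 5.2.4 uses the same phrase with no other definition.
- The grade itself is recorded, so an analyst can regroup the events. This holds for Yes/unlikely entries. It does not recover events of the same kind that another site entered as No/unrelated.
- The pause rule and the reporting of serious events to the sponsor do not depend on the nesting, except that a death is judged by whether it is reasonably attributed, which is not tied to a grade. This stands and limits the point.

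A reader might infer that section 4.5.1 would end a patient's infusions for an unlikely event. The documents do not say so. The event would also have to be Grade 3 to 5, fall within 14 days of infusion and escape the exceptions, and the section opens by saying "Off-treatment criteria mainly apply to eligibility for potential repeat Descartes-11 treatments". The word mainly leaves room for removal during the planned course, so the reading is possible, but it is not a stated rule.

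**Conclusion.** The point holds as a contradiction between the recording item and the protocol's own definition, repeated in Appendix B, together with a missing causality threshold in section 4.5.1. Events judged unlikely can be treated as suspected reactions, can be counted as related, and can be coded differently from site to site. It is a minor correction.

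No size can be given. A reader might infer that related-event rates will be overstated. That cannot be shown: section 6 refers to a separate statistical analysis plan that is not among the text reviewed, no section defines Descartes-11-related by the Yes/No answer, and the share of events graded unlikely is unknown. Nor do the documents available name related-event rates as the principal safety result. Dividing one patient by the planned 34 would not measure the effect either: it gives one patient's share of the sample, and a patient-level rate would move only if that patient had no other event counted as related.

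The conclusion rests on reading section 5.2.4 as written and on applying the definition in 5.1.2 to the same phrase there.

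**What to change.** In section 5.2.4, Appendix B section 4.2.4 and the eCRF code list, move *unlikely* to the No side. Yes then covers possibly, probably and definitely, in line with section 5.1.2. Keep unlikely and unrelated as separate choices under No so that no detail is lost. State in the statistical analysis plan that related adverse events are tabulated on this split.

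Reconcile section 4.5.1 with sections 5.2.4 and 5.5. The sponsor should state which causality grades apply to removal from therapy; that is a clinical decision on which this review takes no position.

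The recording change costs a small wording edit in two places and one code-list update. The threshold in 4.5.1 needs a sponsor decision and one added phrase.

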5.2.5 SAE and SUSAR Reporting

To ensure patient safety, every SAE and SUSAR, regardless of suspected causality, occurring during the adverse event reporting period defined in [Section 5.2.1](#) must be reported to the Sponsor within 24 hours of learning of its occurrence. Recurrent episodes, complications, or progression of the initial SAE must be reported as follow-up information is received. An SAE occurring at a different time interval or otherwise considered completely unrelated to a previously reported one should be reported separately as a new event.

5.2.5.1 Study Sponsor Notification by the Investigator

Any SUSAR and SAE as defined in [Section 5.1](#) must be reported to the Sponsor by **email or fax within 24 hours** of knowledge of the event. To the extent possible, adverse events should be recorded as a diagnosis. Do not list symptoms if a diagnosis can be assigned. At the time of the initial notification, a serious adverse event (SAE) report form should be filled. Following parameters will be asked in the form:

- Subject information
- A description of the event (if there is a diagnosis, it should be included)
- Date of onset

- Current status
- Whether study treatment was discontinued
- The reason why the event is classified as serious
- Investigator assessment of the association between the event and study treatment
- Concomitant medications when the event happened
- Narrative summary of the event

Follow-up information on this event should be reported when received. The follow-up information should describe 1) whether the event has resolved or continues, 2) if and how it was treated, and 3) whether the patient continued or withdrew from study participation.

5.2.5.2 IRB Notification by the Investigator

Following events should be reported to IRB:

- Information that indicates a change to the risks or potential benefits of the research, in terms of severity or frequency. For example:
- Safety monitoring indicates that a particular side effect is more severe, or more frequent than initially expected.
- Change in FDA safety labeling or withdrawal from marketing of a drug, device, or biologic used in a research protocol.
- Breach of confidentiality.
- Change to the protocol taken without prior IRB review to eliminate apparent immediate hazard to a research participant.
- Complaint of a participant when the complaint indicates unexpected risks, or the complaint cannot be resolved by the research team.
- Protocol violation (meaning an accidental or unintentional deviation from the IRB approved protocol) that in the opinion of the investigator placed one or more participants at increased risk or affects the rights or welfare of subjects.

Deaths that occur during the study should be reported within the IRB-specified time frame. For reportable deaths, the initial submission to the IRB may be made by contacting the IRB Director or Associate Director. The AE/Unanticipated Problem Form is required as a follow up to the initial submission.

5.2.5.3 FDA Notification by the Study Sponsor

The Sponsor is required to report certain study events in an expedited fashion to the FDA. These written notifications of adverse events are referred to as IND safety reports. The sponsor must report an IND safety report as described in:

<http://www.fda.gov/downloads/Drugs/GuidanceComplianceRegulatoryInformation/Guidances/UCM227351.pdf>

The following describes the safety reporting requirements by timeline for reporting and associated type of event:

- **Within 7 Calendar Days** any study event that is unexpected, fatal or life-threatening suspected adverse reaction.
- **Within 15 Calendar Days** any study event that is unexpected, suspected adverse reaction that is serious, but not fatal or life-threatening -or- a previous adverse event that was not initially deemed reportable but is later found to fit the criteria for reporting, any finding from tests in laboratory animals that suggest a significant risk for human subjects including reports of mutagenicity, teratogenicity, or carcinogenicity or reports of significant organ toxicity at or near the expected human exposure.

5.3 Medical Monitor

The medical monitor will be a Sponsor physician or Sponsor-appointed physician with appropriate experience and Board Certification to oversee study conduct on the Sponsor's behalf, consult with site investigators, review and synthesize safety information from the various clinical sites, and to apply study-stopping criteria. All decisions by the medical monitor affecting study conduct, including the application of study-stopping or dose-escalation rules, will be documented in the study record.

5.4 Recording of Protocol Deviations

If the impact on the protocol disrupts the study design, may affect the outcome (objectives), or compromises the safety and welfare of the subjects, the deviation must be reported to the medical monitor within three business days. Include the following information on the Sponsor-supplied exception/deviation form: protocol number, subject study number, description of the exception/deviation from protocol and rationale. Ensure all completed exception/deviation forms are signed by the Site Investigator and submitted to the Study Sponsor and medical monitor for review. Once approval of the exception request or acknowledgement of the deviation has been granted by the Sponsor and medical monitor, the exception or deviation will be submitted to IRB and all other applicable committees.

Other deviations should be explained in a memo to file (example: a subject missing a visit is not an issue unless a critical/important treatment or procedure was missed and must have been performed at that specific time).

5.5 Stopping Rules and Study Termination

Premature termination of the clinical trial may occur because of a regulatory authority decision, change in opinion of the IRB or medical monitor. Additionally, recruitment may be stopped for reasons of particularly low recruitment, protocol violations, or inadequate data recording. Specifically, study will be stopped if:

- Study Sponsor or a Regulatory Body decides for any reason that subject safety may be compromised by continuing the study.
- The Sponsor decides to discontinue the development of the intervention to be used in this study.

The study will be **paused if:**

- There is death that is reasonably attributed to study drug within the first 30 days after first infusion
- Two subjects with Grade 4 adverse events to vital organs that are assessed as probably or definitely related to study drug within the 14 days after last infusion

If the study is paused for the reasons above, the PI and members of the study team will meet in person or by teleconference within 24 hours of the event to have a thorough discussion of the event. Meeting minutes capturing the review of any ongoing investigations, including next steps in the management of the subject and any proposed changes to the protocol will be forwarded to the medical monitor. If all parties agree as to the event resolution, then the pause will be lifted. If the study is paused for manufacturing reasons, the Sponsor will make recommendations for process improvements to be implemented. Pending successful completion of a process validation run, the manufacturing pause will be lifted.

6 Statistical Considerations

Statistical analysis will be described in a separate Statistical Analysis Plan.

Briefly, with respect to sample size: the primary endpoint will be the proportion of responders, i.e., patients who are MRD-negative with sCR at the Day 28 Visit. This is an open-label study, and the null hypothesis is that the responder rate will not differ from the natural rate of MRD-negative sCR at the end of consolidation, as observed in the literature. We determined that this natural rate is 10%.^{19,31,64,69-73} For purposes of power calculations, we assume that the response rate will be 35%. With these assumptions, a sample size of 34 will provide 80% power to detect a one-tailed difference at the 95% confidence level.

7 Ethical Considerations

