3.2.1 Overall Treatment Design

The overall schedule of treatment for this Phase II study is illustrated in [Figure 1](#). Steps shown prior to Screening affect eligibility but are not part of the study.

Eligible patients will receive an induction regimen with at least 2 anti-myeloma agents excluding monoclonal antibodies. After completion of the full pre-transplant induction regimen prior to high-dose chemotherapy and ASCT, eligible patients must have measurable residual disease as defined in the Eligibility Criteria. A patient can be screened and enrolled at that point.

Descartes-11 treatment will begin at least 7 days after the patient's final dose of anti-myeloma therapy. The dose of cells will be 25×10^6 cells/kg, and doses will be given on Days 1, 4, 8, 11, 15, 18 (i.e., total dose of 150×10^6 cells/kg). Weight obtained during Screening Visit will be used for dose calculation. Doses are expressed as the number of live CAR+ cells.

After completing all cell infusions, the patient will be evaluated for clinical response and then followed-up for up to 36 months unless they meet off-study criteria outlined in [Section 4.5.2](#). During the follow-up period, if indicated, any additional induction therapy, high-dose chemotherapy and/or ASCT may be administered at the discretion of the investigator. Except for experimental agents that are not approved for myeloma treatment, treatment will be left to the investigator's discretion. The patient will be followed every 3 months for the first year, every 6 months for the second year and one time during the third year.

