3.2.2 Delay of Cell Infusion

Patients experiencing toxicities from their preceding treatments will have their Descartes-11 infusion schedule delayed until these toxicities have resolved to at least Grade 2 (excluding cytopenias), unless in the documented opinion of the medical monitor and treating physician it is reasonable to proceed. During this period, the patient will be assessed to record adverse events and a decision will be made on whether the patient meets criteria for cell infusion. Infusions can also be delayed up to 24 hours for scheduling reasons. Furthermore, prior to study cell infusion, subjects must have been free from fever, infection and organ dysfunction since qualifying for the study (See [Section 3.3.1.2](#) for details). If the patient does not meet infusion criteria, the infusion can be delayed up to 4 weeks.

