3.3 Drug Administration

3.3.1 Preparation and Administration of Study Drug

3.3.1.1 Drug Preparation

3.3.1.2 Drug Administration

Prior to each infusion, patients must meet the following criteria:

1. Temperature is less than 37.9°C;
2. There are no signs of an active infection;
3. Last anti-myeloma agent was given at least 7 days prior
4. Other than a cytopenia, there are no ongoing Grade 2 toxicities from prior treatment precluding cell infusion unless PI documents that is reasonable to proceed, i.e. Grade 2 cough;
5. Pre-infusion clinical assessment does not suggest organ dysfunction and/or rapid disease progression since enrollment.

See [Section 3.2.2](#) for conditions to delay cell infusion and [Section 3.2.1](#) for dose definition. Administered dose must be within $\pm 45\%$ of defined dose. Final dose calculation will be based on actual manufactured cell numbers. Premedication for the cell infusion will be given within 15 to 120 minutes prior to the infusion. The medications are acetaminophen 500-1000 mg orally and diphenhydramine 25-50 mg intravenously or by mouth. **Prior to infusion, the cell product identity label must be double-checked by two authorized staff (MD or RN), and identification of the product and documentation of administration must be entered in the patient's chart as is done for blood banking protocols.** Please see detailed infusion instructions in the Descartes-11 Clinic Storage, Handling and Administration Manual.

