3.3.4 Management of Toxicities

For CAR T-cells, significant toxicities, if any, typically occur within one week of administration and include CRS and neurotoxicity. However, none of these have been observed in patients treated with Descartes-11 and recommendations below are based on published literature and common clinic practice.

The guidelines below are recommendations only and can be tailored to an individual patient's needs based on the judgment of the investigator or treating physician. Management that differs from these recommendations will not be considered a protocol deviation.

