5.1.4 Serious Adverse Event (SAE)

An adverse event or suspected adverse reaction is considered serious if in the view of the investigator or the sponsor, it results in any of the following:

- Death within 30 days of Descartes-11 infusion
- Grade 4 or 5 CRS, infusion reaction, neurotoxicity
- Inpatient hospitalization or prolongation of existing hospitalization (except for protocol-mandated ~24-hour admission for observation due to new-onset fever)
- Persistent or significant incapacity or substantial disruption of the ability to conduct normal life functions
- A congenital anomaly/birth defect
- Important medical events that may not result in death, be life-threatening, or require hospitalization may be considered a SAE experience when, based upon appropriate medical judgment, they may jeopardize the patient or subject and may require medical or surgical intervention to prevent one of the outcomes listed in this definition.

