5.2 Recording of Adverse Events

5.2.1 Adverse Event Recording Period

The study period during which adverse events must be reported is normally defined as the period from the initiation of any study procedures to the protocol therapy completion. For this study, collection of adverse events will begin with enrollment until the subject is off-study. Serious Adverse Event reporting period starts with leukapheresis and ends at 30 days after last Descartes-11 infusion.

All unresolved adverse events should be followed by the investigator until the events are resolved, the subject is lost to follow-up, or the adverse event is otherwise explained. At the last scheduled visit, the investigator should instruct each subject to report any suspected adverse event(s) that might reasonably be related to participation in this study. The investigator should notify the Sponsor of any death or adverse event occurring at any time after a subject has discontinued or terminated study participation if the event may reasonably be related to this study. The Sponsor should also be notified if the investigator should become aware of the development of cancer or of a congenital anomaly in a subsequently conceived offspring of a subject that has participated in this study.

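### The pause rule for a drug-attributed death is timed from the first of six infusions, so it can lapse before dosing ends

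*Combined protocol and SAP*

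**What the plan says.** Section 5.5 lists two events that pause the study. The first is a death: "There is death that is reasonably attributed to study drug within the first 30 days after first infusion". The second is two subjects with Grade 4 vital-organ events "assessed as probably or definitely related to study drug within the 14 days after last infusion".

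The regimen has six infusions (section 3.2.1): "doses will be given on Days 1, 4, 8, 11, 15, 18". Delays are allowed. Section 3.3.1.2 opens its checklist with "Prior to each infusion, patients must meet the following criteria" and refers to section 3.2.2, which says: "If the patient does not meet infusion criteria, the infusion can be delayed up to 4 weeks".

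The other safety windows are not tied to the first infusion. The SAE reporting period in section 5.2.1 "ends at 30 days after last Descartes-11 infusion", and the SAE definition in section 5.1.4 includes "Death within 30 days of Descartes-11 infusion". Section 3.3.4 says that significant CAR T-cell toxicities "typically occur within one week of administration".

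**The concern.** For a single-dose product, a window counted from the first infusion would be natural. Here exposure is repeated, and each dose carries its own risk period. A clock started at dose 1 gives each later dose less cover than the one before, and it does not move when a later dose is postponed.

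Delay can also go with risk. Under section 3.3.1.2 an infusion is withheld for raised temperature, signs of infection or suspected organ dysfunction, and section 1.2.5 describes fever as the usual first symptom of CRS. Under section 4.5.1, fever of any grade and Grade 2 CRS that improves within 72 hours do not end dosing. So a patient who reacted to one dose may be delayed, dosed again, and have less cover left from the death rule.

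At stake is the predefined study-level response to a fatal drug reaction. For an attributed death on, say, Day 33, nothing in section 5.5 requires a pause or the 24-hour team meeting that follows one. Any halt would rest on discretion.

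**Working it through.** **Inputs.** Doses on Days 1, 4, 8, 11, 15 and 18, at 25 × 10^6 cells/kg each, 150 in total (3.2.1). Death window of 30 days from first infusion (5.5). SAE reporting to 30 days after last infusion (5.2.1). Maximum delay of 4 weeks, or 28 days (3.2.2).

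**On schedule**

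- Death window closes: 1 + 30 = Day 31.
- SAE reporting closes: 18 + 30 = Day 48.
- Covered after the last dose: 31 − 18 = 13 of 30 days.
- Not covered: 48 − 31 = 17 of 30 days (57%), Days 32 to 48.

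**With delays after dose 1 totalling d days.** Assume that later doses move with the delayed one and keep their spacing. The last dose then falls on Day 18 + d, and the days covered after it are max(0, 31 − (18 + d)) = max(0, 13 − d). The dose counts below are for a single delay of d days, placed before any one of doses 2 to 6.

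| d (days) | Last dose | Days covered after last dose | Doses given after Day 31 |
|---|---|---|---|
| 0 | Day 18 | 13 | 0 |
| 7 | Day 25 | 6 | 0 |
| 13 | Day 31 | 0 | 0 |
| 14 | Day 32 | 0 | 1 |
| 21 | Day 39 | 0 | 1 to 3 |
| 28 | Day 46 | 0 | 1 to 5 |

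At d = 7 the cover is already shorter than the one-week risk period in section 3.3.4.

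**One 28-day delay, by position**

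- Before dose 2: doses on Days 1, 32, 36, 39, 43 and 46, so 5 fall after Day 31. That is 5 × 25 = 125 of the 150 × 10^6 cells/kg.
- Before dose 3, 4, 5 or 6: 4, 3, 2 or 1 doses fall after Day 31.
- In every case the last dose is 46 − 31 = 15 days after closure.

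**Delay before dose 1.** The window moves with the first infusion, and only the on-schedule gap of 17 days remains.

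**Counting convention.** If the infusion day counts as day 1 of the window, closure is Day 30 and the on-schedule gap is 48 − 30 = 18 days. The range of 1 to 5 doses at 28 days is unchanged.

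**The Grade 4 rule.** Its window ends on Day 18 + 14 = Day 32 on schedule. The term last infusion can mean the final or the most recent one. If it means the final one, related Grade 4 organ events between doses would not count in a patient who goes on dosing. This gap is small: section 4.5.1 stops dosing for most related Grade 3 to 5 toxicity, and criterion 5 of section 3.3.1.2 bars infusion when organ dysfunction is suspected. What is left is mainly the Grade 4 laboratory elevations lasting under 7 days that section 4.5.1 exempts.

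**The case against.** The strongest reply is that Day 31 is a reasonable horizon on schedule. It falls 13 days after dose 6, within a day of the 14-day windows in section 4.5.1 and the Grade 4 rule, and nearly twice the one-week risk period. A stopping window need not equal a reporting window. The product is designed for transient CAR expression, and from the Day 28 assessment other anti-myeloma therapy may start (section 3.4), which confounds attribution of later deaths. This has force: the 17-day on-schedule gap is the weaker part of the point.

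It can also be said that the dose counts are a worst case. They need the full 28 days and preserved spacing, and the protocol does not say how later doses are rescheduled. Much of section 3.2.2 reads as delay of the start of treatment. A long mid-course gap also fits poorly with a response visit at Day 28 ± 3, and the documents do not say whether that visit would move. These are fair limits on the upper figure. But section 3.3.1.2 applies its criteria before every infusion and sends the reader to section 3.2.2 for delays, so mid-course delay is permitted, and 14 days is enough.

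Finally, other safeguards exist. The death would be reported to the sponsor as an SAE within 24 hours, and to the FDA within 7 days if it was an unexpected suspected reaction. The sponsor or regulator may stop the study, and termination may follow from the IRB or medical monitor. The pause itself rests on an attribution judgement and can be lifted by agreement. Section 3.3.4 also reports no CRS or neurotoxicity with Descartes-11 so far. All this lowers the severity, but none of it explains a trigger that can expire while patients are still being dosed.

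**Conclusion.** The concern holds and should be fixed. The first-infusion anchor does not suit a six-dose regimen, and it is out of line with sections 5.1.4 and 5.2.1 and with the Grade 4 rule. On schedule it leaves 17 of the 30 days after the last dose outside the rule, measured against the protocol's own SAE window. Delays after dose 1 totalling 7 days cut into the one-week risk period, and from 14 days the last dose falls after closure. The range of 1 to 5 doses applies at the 28-day maximum with spacing kept. The documents give no frequency for mid-course delays, so how often this would occur cannot be estimated. Uncovered here means outside the predefined pause; reporting duties and discretionary stops still apply. The Grade 4 wording is a secondary point.

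**What to change.** Reword the death rule in section 5.5 to run from first infusion through 30 days after the last infusion received, in line with section 5.2.1. It would then reach Day 48 on schedule and Day 76 after one 28-day delay (46 + 30), and every dose would have at least 30 days of cover. Reword the Grade 4 rule to run from first infusion through 14 days after the last infusion received, so that events between doses count and the term has one meaning.

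The cost is two wording changes in an amendment and a slightly higher chance of a temporary pause, including for deaths after Day 28 when other therapy may have begun. The existing requirement of reasonable attribution to study drug limits that, and a pause can be lifted after review.
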